3.1. Primary Endpoint(s)

The primary endpoints are the PF-7321332 plasma PK parameters described in [Table 2](#).

3.2. Secondary Endpoint(s)

The secondary endpoints include safety endpoints and the ritonavir plasma PK parameters, which are described in Section 3.5 and [Table 2](#), respectively.

CCI

3.4. Baseline Variables

There are no baseline variables to be used as covariates or stratification factors in this study.

Baseline values are those collected on Day 1 prior to the first dosing, or the last pre-dose measurement collected on Day -1.

3.5. Safety Endpoints

3.5.1. Adverse Events

An adverse event is considered a Treatment-Emergent Adverse Event (TEAE) if the event started during the effective duration of treatment. All events that start on or after the first

dosing day and time/start time, if collected, but before the end of the study will be flagged as TEAEs. The algorithm will not consider any events that started prior to the first dose date.

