This is a Phase 1, open-label study to estimate the PK, safety and tolerability of PF-07321332 when PF-07321332/ritonavir is administered in healthy Chinese participants. The study will consist of 1 treatment: multiple oral doses of 300 mg PF-07321332/100 mg ritonavir. A total of approximately 14 healthy male and/or female participants will be enrolled into the study to ensure at least 12 participants will complete the study. Participants who discontinue from the study for non-safety reasons may be replaced at the sponsor's discretion in collaboration with the Investigator.

The total duration of participation in this study is approximately 73 days, including a screening period of up to 28 days to confirm eligibility, treatment duration about 12 days (10 days of dose duration and another 2 days of full PK profile duration) and a follow-up period of approximately 28-35 days post the last dose of study intervention.

Participants will be admitted to the CRU on Day -1 and may be discharged at the discretion of the investigator following completion of assessments per protocol requirement on Day 12 (2 days after last dose on Day 10).

All of participants will receive PF-07321332 and ritonavir together. The dose regimen is PF-07321332/ritonavir 300/100 mg q12h for a total of 19 oral doses (Day 1 to Day 10). The first dose and the last dose will be recommended to be administrated on Day 1 and Day 10 morning, respectively, for intensive PK sample collection.

Following discharge on Day 12 after last PK and safety assessment, follow-up contact may occur via telephone and must occur within 28 to 35 days after the last dose of investigational product, or via on-site visit if it is necessary per investigator's evaluation. Participants who prematurely discontinue for non-safety related reasons may be replaced, at the discretion of the principal investigator and sponsor study team.

Number of Participants

Approximately 14 participants will be enrolled to study intervention.

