8.3.1. Time Period and Frequency for Collecting AE and SAE Information

The time period for actively eliciting and collecting AEs and SAEs ("active collection period") for each participant begins from the time the participant provides informed consent, which is obtained before the participant's participation in the study (ie, before undergoing any study-related procedure and/or receiving study intervention), through and including a minimum of 28 calendar days, except as indicated below, after the last administration of the study intervention.

Follow-up by the investigator continues throughout and after the active collection period and until the AE or SAE or its sequelae resolve or stabilize at a level acceptable to the investigator.

For participants who are screen failures, the active collection period ends when screen failure status is determined.

If the participant withdraws from the study and also withdraws consent for the collection of future information, the active collection period ends when consent is withdrawn.

If a participant permanently discontinues or temporarily discontinues study intervention because of an AE or SAE, the AE or SAE must be recorded on the CRF and the SAE reported using the CT SAE Report Form.

Investigators are not obligated to actively seek information on AEs or SAEs after the participant has concluded study participation. However, if the investigator learns of any SAE, including a death, at any time after a participant has completed the study, and he/she considers the event to be reasonably related to the study intervention, the investigator must promptly report the SAE to Pfizer using the CT SAE Report Form.

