10.3.1. Definition of AE

AE Definition

• An AE is any untoward medical occurrence in a patient or clinical study participant, temporally associated with the use of study intervention, whether or not considered related to the study intervention.• Note: An AE can therefore be any unfavorable and unintended sign (including an abnormal laboratory finding), symptom, or disease (new or exacerbated) temporally associated with the use of study intervention.

Events Meeting the AE Definition

• Any abnormal laboratory test results (hematology, clinical chemistry, or urinalysis) or other safety assessments (eg, ECG, radiological scans, vital sign measurements), including those that worsen from baseline, considered clinically significant in the medical and scientific judgment of the investigator. Any abnormal laboratory test results that meet any of the conditions below must be recorded as an AE:
• Is associated with accompanying symptoms;• Requires additional diagnostic testing or medical/surgical intervention;• Leads to a change in study dosing (outside of any protocol-specified dose adjustments) or discontinuation from the study, significant additional concomitant drug treatment, or other therapy.• Exacerbation of a chronic or intermittent preexisting condition, including either an increase in frequency and/or intensity of the condition.• New condition detected or diagnosed after study intervention administration, even though it may have been present before the start of the study.• Signs, symptoms, or the clinical sequelae of a suspected drug-drug interaction.• Signs, symptoms, or the clinical sequelae of a suspected overdose of either study intervention or a concomitant medication. Overdose per se will not be reported as an AE or SAE unless it is an intentional overdose taken with possible suicidal/self-harming intent. Such overdoses should be reported regardless of sequelae.

Events NOT Meeting the AE Definition

- Any clinically significant abnormal laboratory findings or other abnormal safety assessments that are associated with the underlying disease, unless judged by the investigator to be more severe than expected for the participant's condition.
- The disease/disorder being studied or expected progression, signs, or symptoms of the disease/disorder being studied, unless more severe than expected for the participant's condition.

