- Alternative causes, such as underlying disease(s), concomitant therapy, and other risk factors, as well as the temporal relationship of the event to study intervention administration, will be considered and investigated.
- The investigator will also consult the IB and/or product information, for marketed products, in his/her assessment.
- For each AE or SAE, the investigator must document in the medical notes that he/she has reviewed the AE or SAE and has provided an assessment of causality.
- There may be situations in which an SAE has occurred and the investigator has minimal information to include in the initial report to the sponsor. However, **it is very important that the investigator always make an assessment of causality for every event before the initial transmission of the SAE data to the sponsor.**
- The investigator may change his/her opinion of causality in light of follow-up information and send an SAE follow-up report with the updated causality assessment.
- The causality assessment is one of the criteria used when determining regulatory reporting requirements.
- If the investigator does not know whether or not the study intervention caused the event, then the event will be handled as “related to study intervention” for reporting purposes, as defined by the sponsor. In addition, if the investigator determines that an SAE is associated with study procedures, the investigator must record this causal relationship in the source documents and CRF, and report such an assessment in the dedicated section of the CT SAE Report Form and in accordance with the SAE reporting requirements.

Follow-Up of AEs and SAEs

- The investigator is obligated to perform or arrange for the conduct of supplemental measurements and/or evaluations, as medically indicated or as requested by the sponsor, to elucidate the nature and/or causality of the AE or SAE as fully as possible. This may include additional laboratory tests or investigations, histopathological examinations, or consultation with other healthcare providers.
- If a participant dies during participation in the study or during a recognized follow-up period, the investigator will provide Pfizer Safety with a copy of any postmortem findings, including histopathology.

- New or updated information will be recorded in the originally submitted documents.
- The investigator will submit any updated SAE data to the sponsor within 24 hours of receipt of the information.

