6.6. Safety Summaries and Analyses

6.6.1. Adverse Events

Adverse events will be reported in accordance with the sponsor reporting standards.

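### The TEAE flag uses start date alone, so an adverse event open at first dose that worsens on treatment and stays on its original record is not flagged

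*SAP*

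**What the plan says.** SAP 3.5.1 gives the general definition: "An adverse event is considered a Treatment-Emergent Adverse Event (TEAE) if the event started during the effective duration of treatment". It then flags every event that starts from the first dose (day, and time if collected) until the end of the study, and closes with the exclusion: "The algorithm will not consider any events that started prior to the first dose date". It has no clause for an event that is present before dosing and becomes more severe afterwards, and no other part of the SAP supplies one.

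Protocol 8.3.1 sets the collection period, which "begins from the time the participant provides informed consent". The synopsis describes participation as "including a screening period of up to 28 days to confirm eligibility". Events with a pre-dose onset can therefore be in the database.

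Protocol 10.3.1 lists among the things that count as an adverse event: "Exacerbation of a chronic or intermittent preexisting condition, including either an increase in frequency and/or intensity of the condition". It treats abnormal test results and other safety assessments in a similar way, "including those that worsen from baseline, considered clinically significant in the medical and scientific judgment of the investigator".

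On follow-up, Protocol 10.3.3 says: "New or updated information will be recorded in the originally submitted documents". For the summaries themselves, SAP 6.6.1 says only: "Adverse events will be reported in accordance with the sponsor reporting standards".

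**The concern.** The protocol intends worsening to count as an adverse event, but the SAP flag looks only at when a record starts. The two agree when worsening gets a new record and a new onset date. They part when it is handled as a change to a record that is already open.

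The pre-dose period is not empty. Participants enter the unit on Day -1 and abstain from caffeine and nicotine for 24 hours before dosing (Protocol 5.3.2), and light smokers are eligible (exclusion criterion 18). Minor complaints before the first dose are plausible, and one of them could intensify once dosing begins.

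Safety and tolerability is a secondary objective, and TEAE is the only adverse-event classification that SAP 3.5 defines. An on-treatment worsening left outside the flag would be left out of any table built on it.

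**Working it through.** No figure in the plan depends on this rule, so there is no figure to reproduce. The check is to run the possible cases through SAP 3.5.1 as written.

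| Case | How it is recorded | Result under SAP 3.5.1 |
|---|---|---|
| Chronic or intermittent condition from the history worsens after dosing | New AE under Protocol 10.3.1, onset = date of worsening | Flagged |
| Abnormal test or safety finding at baseline worsens and is judged clinically significant | New AE under Protocol 10.3.1, onset = date of worsening | Flagged |
| AE starts after consent, is open at first dose, worsens on treatment | New record, onset = date of worsening | Flagged |
| Same event | Severity updated on the existing record, pre-dose onset kept | **Not flagged** |
| Event on Day 1 before dosing, no clock time collected | One record dated Day 1 | Not excluded by the last sentence, which uses the date; may be flagged |

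Only the fourth case is lost. Neither document says which of the third and fourth handling applies. The sentence in Protocol 10.3.3 on updated information is compatible with the fourth, but it does not address onset dates.

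**Size, for scale only.** Inputs: about 14 participants enrolled and about 12 evaluable (Protocol 9.5). The safety set is everyone dosed, so 14 is the nearer denominator.

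- One participant whose only qualifying event is unflagged changes a TEAE incidence by 1/n: 1/14 = 7.1 percentage points, or 1/12 = 8.3. This is an upper limit per participant, because someone with another TEAE in the same table row is already counted.
- The documents give no rate for pre-dose events that worsen on treatment. Let p be an assumed probability per participant. The chance of at least one such participant is 1 − (1 − p)^n.

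| Assumed p | n = 14 | n = 12 |
|---|---|---|
| 2% | 1 − 0.98^14 = 24.6% | 21.5% |
| 5% | 1 − 0.95^14 = 51.2% | 46.0% |
| 10% | 1 − 0.90^14 = 77.1% | 71.8% |

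These percentages follow from the assumed p and are not estimates for this trial. They also count every worsening, however recorded; the share that would go unflagged is smaller by an unknown amount.

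**The case against.** The strongest reply is that Protocol 10.3.1 already makes worsening an adverse event, so a correctly completed CRF brings it inside the rule. That stands for exacerbations of preexisting conditions and for worsened findings entered with their own onset date. It does not fully cover an event already open on the CRF at first dose, because nothing in either document requires that record to be closed and re-entered.

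Three further points also stand.

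- CRF completion guidance sits in a separate document (Protocol 10.1.6) that may contain the missing convention. The sentence on updated information in 10.3.3 concerns follow-up and does not say that an exacerbation keeps its old onset.
- A reader might infer that worsened events are lost from the safety summary altogether. The documents do not support that. Protocol 8.3.1.2 has all adverse events from consent recorded on the CRF, and SAP 6.6.1 defers to sponsor standards without limiting the summaries to TEAEs. Only TEAE-based output is at risk.
- A reader might also infer that the rule can only undercount. It cannot be put that strongly. The rule flags events up to the end of the study, with follow-up contact 28 to 35 days after the last dose, and it may flag a Day 1 event that preceded dosing when no time was collected. The worsening gap itself loses events, but the rule as a whole can err either way.

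Finally, participants are overtly healthy, the study has a single treatment and no hypothesis test, and laboratory, vital-sign and ECG data are summarized separately.

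**Conclusion.** The point holds in a narrow form. SAP 3.5.1 states a rule that does not flag an adverse event with onset between consent and first dose that worsens on treatment and stays on its original record, and TEAE-based summaries may miss it. This is more than missing detail, because the SAP states an exclusion and nothing elsewhere in the documents reverses it.

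The size is up to 7.1 percentage points per affected participant with 14 dosed. How many would be affected is unknown and probably small. The conclusion assumes that at least some sites would update the open record, and that the CRF completion guidance and sponsor standards, which are not in the documents, do not already close the gap. It concerns a descriptive secondary summary; the PK endpoints are unaffected. I rate it a cheap improvement.

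**What to change.** Amend SAP 3.5.1 so that an adverse event is treatment-emergent if it starts at or after the first dose, or if it was present before the first dose and increases in severity or becomes serious afterwards.

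State one recording convention for such worsening, and use it throughout:

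- **New record with its own onset date.** The start-date rule then finds the worsening, and the SAP should say that the pre-dose record is not flagged as well.
- **Severity update on the original record.** The CRF must then keep the pre-dose and post-dose severity and the date of change. Protocol 10.3.3 assigns each event to one intensity category, so this would have to be specified.

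Mixing the two could count one worsening twice, on the old record and the new. The first option needs less programming. Either way the cost is a sentence or two in the SAP, a CRF completion note and a small amount of programming, to be settled before analysis.

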3.5.2. Laboratory Data

Safety laboratory tests will be performed as described in the protocol. Baseline is defined as the last pre-dose measurement collected on Day -1.

To determine if there are any clinically significant laboratory abnormalities, the haematological, clinical chemistry (serum), urinalysis, coagulation, TSH and T4 tests will be assessed against the criteria specified in the sponsor reporting standards. The assessment will not take into account whether each participant's baseline test result is within or outside the laboratory reference range for the particular laboratory parameter.

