- c. Participants will be admitted to the CRU on Day -1 and may be discharged on Day 12, following completion of all PK and safety assessment required by protocol, at the investigator's discretion.
- d. Medical history will include a history of prior illegal drug, alcohol, and tobacco use, as well as blood donation within prior 60 days. Medical history will be recorded at Screening and updated on Day -1.
- e. A complete PE will be performed by trained medical personnel at the investigator site at Screening or Day -1 only (height and weight must be obtained at Screening only to obtain BMI for eligibility criteria). A brief PE may be performed at other designated time points at the discretion of the investigator.
- f. Safety laboratory test: should be taken during screening period and Day-1, and should be taken pre-dose (within 30 min before administration) in the morning only during treatment period (Days 2, 5, 8, 10), and taken 48 (\pm 1 hour) hours after last dose of intervention administration on Day 12, with at least 4-hour fasting. Additional safety laboratory assessments may be performed at any time at the discretion of the investigator. Safety laboratory test includes hematology, chemistry, urinalysis and coagulation test (aPTT, PT, INR and fibrinogen).
- g. All thyroid related test should be collected at least once before dosing. Investigator may choose to either collect at screening or Day -1 or both. No fasting requirement for all TSH, free T4 and antibody (aTPO, ATG) testing. Other TSH, free T4, thyroid ultrasound and antibody (aTPO, ATG) tests are permitted to be conducted at any time of the investigator's discretion.
- h. The investigator will discuss with the participant the need to use highly effective contraception consistently and correctly according to contraception guidelines.
- i. For postmenopausal (amenorrheic for at least 12 consecutive months) female participants only.
- j. Urine drug test will be performed at Screening and on Day -1. This test may be performed at any other time at the discretion of the investigator.

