Thyroid function studies	
In 14-day rat toxicology study at high dose of PF-07321332 (1000 mg/kg/day) thyroid gland changes observed were of low severity and without evidence of tissue damage. In the FIH Study C4671001, 3 participants had TEAEs of elevated TSH levels across treatment groups
	TSH and free T4 will be evaluated to monitor thyroid function

PFIZER CONFIDENTIAL

CCI

Potential Risk of Clinical Significance	Summary of Data/Rationale for Risk	Mitigation Strategy
	(PF-07321332 or placebo with ritonavir 100 mg q12h) in the MAD part of the study. There was no clinical correlation with these TSH changes and free T4 remained within reference range at all times.	
Study Intervention(s): Ritonavir		
Gastrointestinal disturbances (including diarrhea, nausea, vomiting and abdominal pain).	Frequently reported adverse reaction in HIV patients at 600 mg BID.	Lower dose of 100 mg twice daily is used in this study. There will be close observation of AEs. If needed, anti-emetics may be provided.
Neurological disturbances (eg, paresthesia, including oral paresthesia, dysgeusia and dizziness).	Frequently reported adverse reaction in HIV patients at 600 mg BID.	Lower dose used in this study. There will be close observation of AEs.
Rash (most commonly reported as erythematous and maculopapular, followed by pruritus).	Frequently reported adverse reaction in HIV patients at 600 mg BID.	Lower dose used in this study. There will be close observation of AEs and monitoring through targeted physical examinations. If needed, palliative care may be provided.
Fatigue/Asthenia.	Frequently reported adverse reaction in HIV patients at 600 mg BID.	Lower dose used in this study. There will be close observation of AEs and monitoring through targeted physical examinations.
Limited case reports of renal toxicity	Although ritonavir therapy is not generally considered nephrotoxic, a limited number of cases of acute kidney injury secondary to ritonavir have been reported post-marketing in HIV patients.	Lower dose used in this study. There will be close observation of AEs and renal function.

PFIZER CONFIDENTIAL

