6.6.2. Laboratory Data

Laboratory data will be listed and summarized in accordance with the sponsor reporting standards. Baseline is as defined in [Section 3.5.2](#).

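### The SAP takes the laboratory baseline from Day -1 only, but the protocol allows TSH and free T4 to be drawn at screening only, so compliant participants can lack a defined thyroid baseline

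*SAP*

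**What the plan says.** **SAP.** Section 3.5.2 sets the laboratory baseline: "Baseline is defined as the last pre-dose measurement collected on Day -1". The same section covers the thyroid tests: "urinalysis, coagulation, TSH and T4 tests will be assessed against the criteria specified in the sponsor reporting standards". Section 3.4 gives the general rule: "Baseline values are those collected on Day 1 prior to the first dosing, or the last pre-dose measurement collected on Day -1". Neither rule accepts a screening value. Section 6.6.2 says "Laboratory data will be listed and summarized in accordance with the sponsor reporting standards" and points back to section 3.5.2 for the baseline.

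**Protocol.** The Schedule of Activities grid (section 1.3) marks TSH and free T4 at both screening and Day -1. Footnote g, attached to that row, relaxes this: "All thyroid related test should be collected at least once before dosing", and then "Investigator may choose to either collect at screening or Day -1 or both". Screening runs from Day -28 to Day -2. In the risk table of section 2.3.1, thyroid function is a listed potential risk, and the mitigation given is "TSH and free T4 will be evaluated to monitor thyroid function".

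**The concern.** The collection rule and the analysis rule do not fit together. The protocol treats a screening draw as sufficient; the SAP does not recognise it as a baseline. A site can follow the protocol exactly and still leave participants without a baseline for these two analytes.

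This matters because thyroid function is one of the risks the protocol names. It reports TSH increases in 3 participants in the multiple-dose part of the first-in-human study, across groups given PF-07321332 or placebo with ritonavir. The present study has one arm and no placebo, so a participant's own pre-dose value is the only comparator within the study. Under the rule as written, any laboratory summary that refers to baseline would have gaps for TSH and free T4 although a usable pre-dose measurement exists.

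**Working it through.** The plan states no figure to reproduce here: it tests no hypothesis and gives no count of expected baselines. The check sets the permitted collection patterns against the SAP rule.

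**Inputs**
- Planned enrolment: about 14 (Protocol section 9.5).
- Pre-dose thyroid draws: at least one, at screening, Day -1 or both (footnote g).
- Baseline rule: Day -1 (SAP 3.5.2), or Day 1 pre-dose or Day -1 (SAP 3.4).

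**Could another scheduled draw fill the gap?** Footnote f requires the routine safety panel at screening and on Day -1, so the Day -1 rule works for that panel. But the footnote limits the panel to hematology, chemistry, urinalysis and coagulation; thyroid tests are not in it. Its treatment-period draws are given as Days 2, 5, 8 and 10, so it lists no pre-dose draw on Day 1. The grid columns in the copy reviewed are not reliably aligned, but a Day 1 mark for this panel would make no difference, since the panel has no thyroid tests. Footnote g allows extra thyroid tests at the investigator's discretion, but schedules none.

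**Patterns**

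| Thyroid draw before dosing | Compliant with footnote g | Baseline under SAP 3.5.2 or 3.4 | Baseline if the last pre-dose value is used |
|---|---|---|---|
| Screening only | Yes | No | Yes |
| Day -1 only | Yes | Yes | Yes |
| Both | Yes | Yes | Yes |

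**Count.** Let k be the number of participants drawn at screening only. The number with a SAP-defined baseline is 14 - k:
- k = 0: 14 - 0 = 14 of 14
- k = 7: 14 - 7 = 7 of 14
- k = 14: 14 - 14 = 0 of 14

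With the last pre-dose value accepted, all 14 compliant participants have a baseline, whatever k is.

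**Age of the baseline after that change, assuming no Day 0.** A Day -1 value is 1 day before Day 1. A screening value is 2 days (Day -2) to 28 days (Day -28) before Day 1. It can be older only where the delay allowance in Protocol section 8 is used.

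**Is the screening value available?** Protocol section 9.3.3 treats screening data used for eligibility, laboratory data included, as source data that need not be reported unless the plan says otherwise. If screening thyroid results fall under that sentence, changing the definition alone may not be enough; the SAP must also say that these values are kept for analysis.

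**The case against.** The mismatch in the text is hard to dispute; the case on the other side is that little follows from it.

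- **No laboratory table in the SAP is shown to need this baseline.** The SAP specifies change from baseline for vital signs and ECG but not for laboratory data. The abnormality check in section 3.5.2 disregards whether the baseline was within the reference range. This stands, and it limits the effect. Section 6.6.2 nevertheless ties the laboratory summaries to the section 3.5.2 baseline, so the definition is meant to be used.
- **The sponsor reporting standards may contain a fallback.** They are not in the documents, so this cannot be excluded. None is stated, and the explicit Day -1 rule points the other way.
- **Screening-only collection may never happen.** The grid marks both visits, participants are admitted on Day -1 with a safety draw that day, and thyroid tests need no fasting. So k = 0 is entirely possible, and the range of 0 to 14 is not an estimate. It is still a choice that the protocol leaves open.
- **Participant-level monitoring does not depend on the SAP definition.** The investigator reviews each laboratory report and can use any pre-dose value. This is correct: what is at risk is the reported summary, not the monitoring.

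**Conclusion.** The concern holds. The SAP's baseline rule excludes a pre-dose thyroid value that the protocol accepts as sufficient. Between 0 and 14 of about 14 participants could be affected. The number depends wholly on the site's choice, and replacement participants could raise the denominator.

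The confidence is in the contradiction itself. Its effect on output depends on what the sponsor reporting standards require for laboratory data. At most, baseline-referenced TSH and free T4 summaries would be incomplete. Post-dose values would still be listed and checked against the abnormality criteria, and the PK analyses do not change. This is a secondary, descriptive matter that should be corrected; it does not threaten the study's main results.

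**What to change.** In SAP section 3.5.2, define the TSH and free T4 baseline as the last non-missing measurement before the first dose, including screening, and amend section 3.4 to match. State in the SAP that screening TSH and free T4 results are to be held in the analysis database, which supplies the exception that Protocol section 9.3.3 leaves room for. List the study day of each thyroid baseline so that older values are visible. The Day -1 rule can stay as it is for the routine safety panel.

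The cost is one sentence in section 3.5.2, its counterpart in section 3.4, and a check that screening thyroid results are transferred. No procedure is added for participants. The drawback is baselines of mixed age: 1 day for some participants, 2 to 28 days for others, and more under the delay allowance.

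The alternative is to make the Day -1 draw already marked in the grid compulsory. That would also give every compliant participant a baseline, and of uniform age, but it means changing footnote g in the protocol and removing the investigator's option.
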